The proposed study will use parallel-groups, randomized, sham controlled, double-blinded design in which 36 participants with motor incomplete SCI (AIS B – D level) will randomly assigned to receive tDCS combined with repetitive arm training (RAT) or sham tDCS combined with R-A training. During the first 20-minute participants (n=24) in the experimental group will receive 20 minutes of anodal tDCS (2 mA) on motor cortex contralateral to their trained side followed by RAT for 60 minutes. Participants (n=12) in the control group will receive 20 minutes of sham tDCS followed by RAT for 60 minutes. In the sham stimulation 2 mA of anodal current will be delivered in a ramp up and down fashion for 30 seconds at the beginning and 30 seconds at the end of 20 minutes of stimulation. Treatment will be administered at an intensity of 5 sessions per week for 2 weeks.

The randomization schedule will be provided by project statistician ([name]).

Outcome measure:

Feasibility outcome measure: Adherence with therapy will be measured as;
(1) the number of treatment sessions attended by each participant,
(2) number of drop-outs in each group,
(3) participant's perceptions of the use of study implementation (using the tDCS and exercise equipment, numerical rating scale with 'not difficult at all' at 0, and 'very difficult' at 10)
(4) participant's perceptions of usefulness of the intervention (numerical rating scale with 'not at all useful' at 0 and 'very useful' at 10).

The telerehabilitation intervention will be considered as feasible if at least 80% adherence rate is achieved (completed number of sessions \geq 8 out of 10), if attrition rate is no higher than 10% in each study group, if at least 40 minutes of 60 minutes exercise session is completed and if no serious adverse events took place (other than expected side effects from tDCS).

Clinical outcome measure: Primary clinical outcome measure is GRASSP prehension performance (Kalsi-Ryan et al., 2012). Secondary clinical outcome measures are grip strength and Spinal Cord Injury Independence Measure (SCIM III) (Itzkovich, Gelernter et al. 2007). Assessments will be repeated immediately after completion of 10 sessions and at 4-weeks follow-up.

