Brain motor cortex function: Functional near-infrared spectroscopy (fNIRS) device will be used to measure and record relative changes in oxygenated and deoxygenated hemoglobin from the motor cortex of the brain. This in turn will help examine and understand the effects of a combined tDCS/robotic assisted arm training treatment upon motor-related brain activity. FNIRS emits near-infrared light (740nm/850nm) into the head and acquires the amount of light returning using a detector positioned 3cm from the light source. It is a portable, non-invasive device similar to EEG and has been used in multiple research studies investigating brain function under various task-oriented settings. One major risk the fNIRS device poses is potential eye damage if the infrared light-emitting diodes (IR LEDs) are shined into an individual's eyes for an extended amount of time. This will be mitigated however by ensuring that the investigator leaves the device powered off before placing it on the user's head. An additional minor risk includes a mild discomfort caused by the tightness of the headband and straps. The investigator will adjust the device to provide optimal comfort to the subject. fNIRS will be performed at the baseline, immediately after completion of 10 sessions treatment and at 4-week follow-up.

5. Study Population:

36 adults with chronic incomplete cervical SCI will be recruited from TIRR/Memorial Hermann, local healthcare providers and from support groups in Houston area.

Participants will be included if they have:

- (1) diagnosis of a chronic incomplete cervical lesion as defined by the American Spinal Injury Association Impairment scale classification and at least for 6 months post injury;
- (2) upper-extremity weakness associated with tetraplegia with minimal residual thumb and index finger movement sufficient to grip small objects such as marble;
- (3) age 18 - 70 years;
- (4) no brain injury;
- (5) no planned alteration in upper-extremity therapy or medication for muscle tone during the course of the study;
- (6) no contradiction to tDCS
- (7) access to internet at home.

Subjects will be excluded if they have:

- (1) prior history of seizure;
- (2) modifications in chronic use of neuroactive medication (e.g., neurostimulants, anticonvulsants, or antidepressants) during study period (between baseline and follow-up);

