Schedule of activities

Event	Baseline (Day -6 to 0)	Treatment Sessions (1-10)	Post-treatment (Day 5±3)	Follow-up 1 (Day 35±5)
Informed Consent	X			
Inclusion/Exclusion Criteria	X			
Demographics	X			
Medical and Social History	X			
Medication Checklist	X		X	X
ASIA-Impairment Scale	X		X	X
GRASSP	X		X	X
Grip Strength				
NHPT	X		X	X
SCIM-II	X		X	X
tDCS	X			
Music Glove and FitMi arm training		1-10		
tDCS-Side Effects Questionnaire		1-10		
Pain and Fatigue		1-10		
Participant-tDCS &Arm Exercise Survey		1,6,10		
Participant- Usefulness of Intervention Survey			X	X
Caregiver tDCS&Arm Exercise Survey		1,6,10		
Caregiver-Usefulness of Intervention Survey			X	X

Post-treatment and Follow-Up Assessment (Duration: two-hours): During this period subjects will be asked to come within a-week after they have completed the study and at week 4 for follow-up. GRASSP, Grip Strength, SCIM-II and fNIRS measurements will be repeated at post-treatment visit and at 4-week follow-up visit.

7. Potential Risks/Discomforts

tDCS: Transcranial direct current stimulation (tDCS) is a technique that poses a non-significant risk to subjects. The safety of this technique has been addressed and tested by multiple researchers (e.g., Hummel, et al., (Hummel and Cohen, 2005); Fregni, et. al., (Fregni et al., 2006a, Iyer et al., 2005); Nitsche, et al., (Nitsche et al., 2003c, Nitsche et al., 2003b, Nitsche et al., 2003a), (Nitsche et al., 2004); Priori, et al., (Priori, 2003)). Researchers have concluded that tDCS, as applied in a manner similar to our proposed protocol, induces only temporary mood, cognitive / motor effects, and no negative side effects. No undesirable or long-lasting effects have been reported, nor have any subjects reportedly abandoned a study due to discomfort. The most common side effects according to a recent consensus are: headache, dizziness, nausea, itchy sensation as well as irritation under the area of the electrodes (Nitsche et al., 2008). Researchers at the National Institute of Neurological Disorders and Stroke (NINDS), Iyer et al., (2005) (Iyer et al., 2005) conducted a safety study on tDCS, investigating 20-minute sessions of 1 mA and 2 mA current stimulation with healthy controls (n=103). No negative effects were identified. Nitsche and colleagues (2004) found no measurable structural changes in brain tissue due to tDCS (Nitsche et al., 2004). Finally, two recent studies showed that

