several sessions of tDCS are safe to be used in chronic pain syndromes such as fibromyalgia and spinal cord injury (Fregni et al., 2006c), (Fregni et al., 2006a). Thus, a growing body of research from different laboratories has shown that tDCS is a safe, noninvasive and painless technique for modulating neural excitability, with measurable but only transient effects.

The current protocol uses stimulation level of 2mA and a duration of 20minutes which falls within safety limits published by numerous clinical studies applying tDCS with human subjects. In our lab at Neurorecovery Research Center at TIRR, we completed several tDCS studies (HSC-MS-12-0868, HSC-MS-15-0269, HSC-MS-14-0354) and did not observe any serious side effects that required termination of subject's treatment program. As expected, tingling was the most common transient symptom followed by skin redness. Both are physiological responses to direct current stimulation and require no medical action.

The safety of tDCS in the pediatric and pregnant population has not been assessed. Therefore female subjects will be questioned for pregnancy at the screening, and pregnant women will be excluded. If a subject becomes pregnant during the course of the study, they will be withdrawn from the study.

Arm Exercise- Training: Patients with spinal cord injury sometimes develop pain or discomfort in the shoulders and arm. Subjects will be questioned for fatigue or discomfort during training sessions, and frequent breaks will be given to mitigate muscle fatigue. If any discomfort related to prolonged sitting happens, the training will be paused and participant will be encouraged to change his/her sitting position (weight shifting).

If there is evidence that pain or fatigue is worsened by the therapy, the sessions will be reduced or discontinued. All therapy sessions will be supervised and monitored by [name].

Assessment/Questionnaires: All assessments will be performed in a designated room inside NeuroRecovery Research Center at TIRR Memorial Hermann. None of these tests are either painful or uncomfortable to perform. In order to prevent potential embarrassment during the testing the test will be done individually and in private. If subjects feel uncomfortable in answering any of the questions they may stop the study at any time.

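### Participants whose sessions are discontinued early have no stated post-treatment or follow-up assessment, and the sections time that visit differently

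*Combined protocol and SAP*

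**What the plan says.** The timing of the post-treatment visit appears in five places in the protocol.

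- **Section 4, clinical outcome measure:** "Primary clinical outcome measure is GRASSP prehension performance", and "Assessments will be repeated immediately after completion of 10 sessions and at 4-weeks follow-up".
- **Section 4, brain motor cortex function:** fNIRS is taken at baseline, then "immediately after completion of 10 sessions treatment and at 4-week follow-up".
- **Section 6, narrative on post-treatment and follow-up assessment:** "subjects will be asked to come within a-week after they have completed the study", with a further visit at week 4.
- **Section 6, schedule of activities:** GRASSP is marked at baseline, at a post-treatment column headed Day 5±3 and at a follow-up column headed Day 35±5. No session count is attached, and the day from which these are counted is not given.
- **Section 9, data analysis:** the GRASSP contrast is the change from baseline to just after treatment, again without a session count.

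The plan also foresees incomplete treatment. Under the feasibility outcome in section 4, the intervention is "considered as feasible if at least 80% adherence rate is achieved", defined as 8 or more of 10 sessions, and "if attrition rate is no higher than 10% in each study group". Section 7, under arm training, says: "If there is evidence that pain or fatigue is worsened by the therapy, the sessions will be reduced or discontinued".

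No section says whether missed sessions are made up, whether someone who stops treatment stays in assessment, which participants form the analysis population, or how missing GRASSP values are handled.

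**The concern.** Three of the five statements time the visit by completing something: ten sessions in two places, the study in the third. A site that follows that wording has no visit to book for a participant whose sessions were stopped part-way, and no date from which to count four weeks.

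That participant would then have no post-treatment GRASSP value and would drop out of the change-score test in section 9. The active-versus-sham comparison would become one among people who finished treatment. Finishing is decided after randomisation and partly by how well the programme is tolerated, so the comparison would no longer rest on randomisation alone. With 24 and 12 participants, each loss also costs precision, most of all in the sham arm. A measurement that was never taken cannot be recovered at analysis.

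**Working it through.** **1. The plan's own figures.** Sessions: 5 per week × 2 weeks = 10. Adherence threshold: 8/10 = 80%. Allocation: 24 + 12 = 36. All three agree with section 4. A participant can therefore count as adherent with 8 or 9 sessions, short of the ten named in the assessment wording.

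**2. Which day the schedule counts from.** Day 5±3 covers Days 2 to 8. If the first session is on a Monday, called Day 1, the tenth falls on the second Friday, Day 12. Counted from the first session, Days 2 to 8 lie inside treatment. Counted from a baseline at Day 0, with sessions starting the following week, session 10 is no earlier than Day 12, so Days 2 to 8 again precede the end of treatment. The column appears to mean days after treatment ends. The only marker the text gives for that end is completion of ten sessions.

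**3. Two participants run through the five statements.**

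| Statement | 8 or 9 sessions over the full two weeks | Sessions discontinued early, for example after the fourth |
|---|---|---|
| Section 4, clinical measures | Ten not reached if read as a condition; visit due if read as timing | Ten not reached; no date |
| Section 4, fNIRS | Same | Same |
| Section 6, narrative | Course has run out, so a visit can be read in | Unclear whether this person completed the study |
| Section 6, schedule | Visit marked; end of the two weeks is a usable anchor | Visit marked, but from the last session received, the scheduled last day, or neither |
| Section 9 | Change just after treatment can be formed | No date to which just after treatment refers |

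The first column has a workable reading. The second has none that the text supports over the others. The four-week follow-up has the same gap.

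**4. Effect on precision.** The standard error of the between-arm difference, in units of a common standard deviation, is sqrt(1/n1 + 1/n2).

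- All randomised: sqrt(1/24 + 1/12) = sqrt(0.1250) = 0.354.
- Losses at the 10% limit: 10% of 24 is 2.4, so at most 2; 10% of 12 is 1.2, so at most 1. With 22 and 11: sqrt(1/22 + 1/11) = sqrt(0.1364) = 0.369.
- Ratio: 0.369/0.354 = 1.04.

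**5. Effect on bias.** This would need the number of early stoppers in each arm and how their GRASSP change differs from that of completers. The documents give neither, so no figure can be computed.

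**The case against.** The strongest reply is that completion of ten sessions is simply a way of saying when the course ends. There is one course, ten sessions over two fixed weeks, and no section says that people with fewer sessions are not assessed. The schedule marks GRASSP for everyone without a session condition, and section 9 speaks only of the end of treatment. This stands for participants with 8 or 9 sessions. A reader might infer that they have no post-treatment visit as written; the schedule and section 9 do not support that. A reader might also try to count how many adherent participants would be lost. Such a count needs attendance rates the documents do not give, assumes that missed sessions are never made up, and assumes the strict reading just set aside.

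The reply is also right that differential loss is not documented. Section 7 reports no serious side effects requiring termination in the group's earlier tDCS studies, section 6 describes a sham that mimics the initial sensation, and the pain and fatigue rule concerns arm training, which both arms receive. The 8-of-10 and 10% figures are feasibility criteria, not predicted rates. A claim that the result will be biased in a given direction is therefore not supported.

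Finally, the mixed model in section 9 can use incomplete series. That helps only where some post-baseline GRASSP exists. The schedule marks GRASSP at baseline, post-treatment and follow-up only, so a person who attends neither later visit contributes nothing on change.

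What remains unanswered is the early stopper: no section keeps that person in assessment or dates the visits.

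**Conclusion.** The concern holds in a limited form. The timing statements in sections 4, 6 and 9 differ and need reconciling. For participants whose sessions are discontinued early, the plan provides no post-treatment or follow-up assessment and no date to count from. If sites follow the completion-based wording, the primary change-score contrast is confined to completers.

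The size is modest on what can be computed: about a 4% rise in the standard error if losses reach the attrition limit in both arms, assuming equal standard deviations. This is an illustration, not a ceiling, because the plan does not say whether discontinuing sessions counts as dropping out. Any bias is of unknown size and direction. This is an inexpensive improvement worth making prospectively; it is not a defect that invalidates the design of a 36-person study whose first aim is feasibility.

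**What to change.** Reconcile sections 4 (clinical and fNIRS paragraphs), 6 (narrative and schedule) and 9 so that they say the same thing:

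- Post-treatment and four-week follow-up assessments are sought from every randomised participant who has not withdrawn (or been withdrawn) from the study or refused assessment, whatever number of sessions was received. The exception is needed because section 7 withdraws participants who become pregnant and lets subjects stop at any time.
- Both visits are timed from one stated anchor: the scheduled last day of the two-week treatment period or, if make-up sessions are permitted, the last made-up session. The schedule's day numbers are defined from that anchor.
- Stopping or reducing sessions does not by itself end assessments.
- The number of sessions received is recorded as a separate variable.

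The cost is protocol wording. No new type of visit is added, and section 15 already reimburses each assessment visit. The small downside is that some participants will be assessed after fewer sessions, which dilutes the apparent effect. That is the price of keeping the comparison as randomised.

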Data for feasibility and adherence will be analyzed using descriptive statistics. For effectiveness, difference in GRASSP score in active arm and between active vs sham arm (immediately after treatment - baseline) will be analyzed with paired t test (if the normality is satisfactory with Kolmogrov-Smirnov test). If the K-S test suggests skewed distribution, we will conduct Wilcoxon signed rank test and Wilcoxon rank sum test for these two analyses.

In multivariable analysis, we will fit a mixed model for data collected at baseline and ten sessions and at 30-days follow-up in both study arms. Patient will be included as random effect of the mixed model. The fixed effects include treatment arm (active, sham) and time (0 for baseline, 1-10 for ten sessions). First, we will consider time levels as nominal and test interaction between treatment and time. The interaction will be added if it will be significant. Second, we hope to parametrically model time. The mean trajectory plot will guide us on the parametric form of time. Our emphasis will be linear time and 3rd-order polynomial time. We tend to favor the 3rd-order polynomial time as we believe that the GRASSP score will increase greatly for the first few sessions and then become stable.

In mixed model analysis, besides incorporating patient random effect, we will also test if there exists stronger correlation among measurements with shorter time intervals. We will specify a few serial correlation patterns including exponential, Toeplitz and banded Toeplitz. The random effect specification will be extended to incorporate random time slope. We will fit all these models and report AIC values to guide our decision on covariance pattern.

10. Potential Benefits

The results of these studies may benefit subsequent future subjects if remotely supervised, home-based combined tDCS and repetitive arm training proves to be effective when compared to repetitive arm training only.

The benefits of participating in this study may be improved arm and hand movement. However, there may be no benefit from participating in this study.

11. Risk-Benefit Ratio:

The potential improvement of arm and hand movement outweighs the risk of non-invasive brain stimulation, fatigue, pain and discomfort.

12. Consent Procedures:

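### The difficulty and usefulness ratings, two of the four listed feasibility measures, are not collected when someone stops early and may look too favourable, although the feasibility decision rule does not use them

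*Combined protocol and SAP*

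**What the plan says.** Section 4 (Study Design) lists four feasibility measures: "the number of treatment sessions attended by each participant", "number of drop-outs in each group", "participant's perceptions of the use of study implementation" and "participant's perceptions of usefulness of the intervention". The last two are 0–10 ratings, one of difficulty and one of usefulness.

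The Schedule of activities in Section 6 places "Participant-tDCS &Arm Exercise Survey" at sessions 1, 6 and 10, and "Participant- Usefulness of Intervention Survey" at the post-treatment and follow-up visits only. Judging by their names, these surveys carry the third and fourth measures. The caregiver versions have the same timing but are not among the four listed measures.

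The text under the schedule ties the post-treatment visit to having finished, and Section 4 ties the clinical assessments to the end of the ten sessions. The schedule has no column for withdrawal or early stopping, and no section asks for the reason for stopping. On analysis, Section 9 says "Data for feasibility and adherence will be analyzed using descriptive statistics". It gives no denominator and no rule for missing ratings.

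Section 4 also sets a rule for calling the programme feasible: adherence of at least 80% (8 of 10 sessions), attrition of at most 10% in each group, at least 40 of the 60 exercise minutes, and no serious adverse events. Neither rating is part of that rule.

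**The concern.** Aim 1 asks whether a home programme is feasible when a caregiver has to position the stimulation, run the device and the laptop, and help with the exercise equipment. The counts of sessions and drop-outs show that people left. They do not show whether the burden of the equipment was the cause. The two ratings are the listed measures that could speak to this.

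A participant who stops at session 3 gives one first-day difficulty score and, unless recalled outside the plan, no usefulness score. The first-day score cannot capture difficulty that builds up later, and Section 6 says that the exercises become harder over the course. Early stopping is foreseen: Section 7 allows sessions to be reduced or discontinued for worsening pain or fatigue, and lets subjects stop at any time.

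If those who leave are less satisfied, the session 6 and 10 difficulty ratings will be too low and the usefulness ratings too high. A rating not taken at the time cannot be recovered in the analysis.

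**Working it through.** The plan gives no figure for these ratings, so there is nothing to reproduce. The check is how far unrated leavers could move a mean.

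**Inputs from Section 4:** 24 active and 12 sham participants (24 + 12 = 36); attrition limit 10% in each group; rating scale 0–10.

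**Inputs assumed (not in the documents):** mean difficulty 3 in those who stay and 6 to 10 in those who leave, with 9 as the central case. For usefulness, 8 in those who stay and 2 in those who leave.

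**Step 1. Drop-outs that the rule permits.** The largest whole number not above 10% of the arm:
- Active: 0.10 × 24 = 2.4, so 2 (2/24 = 8.3%). A third gives 3/24 = 12.5% and fails.
- Sham: 0.10 × 12 = 1.2, so 1 (1/12 = 8.3%). A second gives 2/12 = 16.7% and fails.
- Together at most 3. Any 4 drop-outs must breach the limit in at least one arm.

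**Step 2. Shift in the mean when k of n leavers are unrated.** Shift = (k/n) × (leaver mean − stayer mean).
- Arithmetic maximum in an arm at its limit (gap of 10 points): 2/24 × 10 = 1/12 × 10 = 0.83 points.
- Assumed 6-point gap, both arms together, k = 3: 3/36 × 6 = 0.5 points. For difficulty, (33 × 3 + 3 × 9)/36 = 3.5 against 3.0 in stayers. For usefulness, (33 × 8 + 3 × 2)/36 = 7.5 against 8.0.
- Range of gaps from 3 to 7 points at 8.3% loss: 0.25 to 0.58 points.

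**Step 3. Heavier losses.** With the same 6-point gap, 4 of 36 gives 0.67 points and 6 of 36 gives 1.0 point. By Step 1 the attrition criterion has already failed in both cases, so the programme would not be called feasible.

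**Step 4. Fixed session numbers.** A participant can miss 2 of the 10 sessions and still meet 8 of 10. There are C(10,2) = 45 such patterns, and C(8,2) = 28 of them avoid both session 6 and session 10. The other 17 (38%) miss at least one of those sessions. This counts patterns and is not a probability. It shows that an adherent participant can also lack a scheduled difficulty rating, so the number rated has to be reported.

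**The case against.** The strongest case against is that little depends on these ratings. The first two listed measures count those who leave, and the decision rule uses neither rating. A session 1 difficulty score is scheduled for everyone who starts, and side-effect, pain and fatigue forms are scheduled at every session. All sessions are supervised live by video, so equipment problems will be seen. The schedule does not bar someone who stopped from the post-treatment visit; it is silent. Leavers need not be dissatisfied either: Section 7 also names pregnancy as a reason for withdrawal. Finally, pooling a usefulness score after three sessions with scores after ten would mix different exposures.

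Most of this stands. A reader might infer that feasibility as a whole is judged only on those who stayed, or that the programme could be called feasible because dissatisfied people went unrated. The documents do not support either reading, because leavers count against adherence and attrition. The direction of the bias is an assumption, and last ratings should not be pooled into one mean.

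The objection does not remove the gap. The symptom forms do not ask about difficulty with equipment or about usefulness, and being observed on video is not a recorded rating. The first-day score does not explain a later decision to stop. Silence about the post-treatment visit means that nobody is instructed to recall a person who has left.

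**Conclusion.** The point holds for the two ratings and no further. As the plan is written, the later difficulty ratings and all usefulness ratings will come mainly from those who stayed, with no denominator and no exit information. They may look too favourable if leavers are less satisfied, which is plausible but assumed.

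The size is modest while the attrition criterion is met: at most 0.5 points overall under an assumed 6-point gap, and never more than 0.83 points in an arm. These limits take everyone who stops early to be counted as a drop-out. Someone who stops the sessions but still attends the visits would give a usefulness rating, but no difficulty rating after the last scheduled survey reached.

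This is a cheap improvement to data collection for two Aim 1 measures. It does not show a flaw in the feasibility decision.

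**What to change.** **Schedule of activities (Section 6).** Add a time point for the last session or stopping of treatment. For anyone who stops early, collect the existing participant and caregiver difficulty and usefulness surveys and the main reason for stopping, by the video link already in use or by telephone.

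**Data analysis (Section 9).** Report each rating by arm and time point with the number rated out of the number randomised. Show the exit or last available ratings of those who stopped separately, next to the completers' ratings and with the number of sessions received. Do not pool them into one mean.

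**Cost.** One schedule column and a few minutes for each person who stops. Some will decline, so the gap will shrink but may not close, and the reported ratings may look slightly less favourable.

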- (3) any joint contracture or severe spasticity in the affected upper extremity, as measured by a Modified Ashworth Score \geq than 3 out of 4.

6. Study Procedures:

Baseline Assessment (Duration: two to three hours): For both SCI subjects and healthy volunteers, the baseline assessment can be on the same visit as screening and will be performed in the Motor Recovery Laboratory by an evaluator blinded to subject's group assignment. Subjects (SCI) will be evaluated for upper extremity motor functions. Arm and hand functions will be assessed with Graded Redefined Assessment of Strength, Sensibility and Prehension (GRASSP), ASIA upper extremity scale (motor and sensory), grasp and release test and independence in daily functions will be assessed with SCIM-II.

Caregiver training: On the day of in-clinic baseline assessment, caregiver/family member who will be delivering the therapy at home will be trained on intervention protocol (localization of primary motor cortex to deliver the tDCS, operating the tDCS machine, operating the laptop and videoconference system, using special exercise equipment). Then they will take the tDCS device, exercise equipment and lap top computer home.

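### Minor: Section 7 withdraws a participant who becomes pregnant from the whole study, for a reason that concerns tDCS only, and so gives up later outcome data and adds a protocol-imposed loss to a tight attrition criterion

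*Combined protocol and SAP*

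**What the plan says.** The rule stands in Section 7 (Potential Risks/Discomforts), under tDCS. Its reason is "The safety of tDCS in the pediatric and pregnant population has not been assessed". Two consequences follow. At entry, "female subjects will be questioned for pregnancy at the screening, and pregnant women will be excluded". After entry, "If a subject becomes pregnant during the course of the study, they will be withdrawn from the study".

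Section 6 and the schedule of activities place two assessment visits after the tenth and last session: post-treatment (Day 5±3) and follow-up (Day 35±5, also called the 4-week visit). The text below the schedule has GRASSP, grip strength, SCIM and fNIRS repeated at both. The tDCS side-effects form and the pain and fatigue form are scheduled for sessions 1 to 10 only.

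Section 4 counts drop-outs per group as a feasibility outcome and sets a 10% ceiling on attrition in each arm, with 24 participants in the active arm and 12 in the sham arm. It also requires that no serious adverse event occurs, with no end date. Section 9 bases the main effectiveness analysis on the GRASSP change from baseline to just after treatment, and brings the follow-up visit into a mixed model.

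The list in Section 5 that begins "Subjects will be excluded if they have" has three items: "prior history of seizure", "modifications in chronic use of neuroactive medication" and "any joint contracture or severe spasticity in the affected upper extremity". Pregnancy is not among them.

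**The concern.** The reason and the rule differ in scope. The reason is about receiving stimulation; the rule ends everything, assessments included. Because it runs for the whole course of the study, it also covers the weeks after session 10, when no stimulation is left to stop and only assessments remain. Nothing in the protocol separates stopping treatment from ending data collection, keeps a withdrawn participant in assessment, or says how her data are analysed. Loss of all later data is therefore the plain reading.

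Two things are at stake. One is outcome data from a randomised participant in a trial of 36. The other is how the feasibility result is read: a withdrawal that the protocol itself imposes says little about whether home telerehabilitation is workable, but nothing stops it from counting towards the attrition limit.

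**Working it through.** The documents give no pregnancy rate, alpha, effect size, standard deviation or sample-size calculation, so there is no stated figure to reproduce. The steps below show only how much one such withdrawal could matter.

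**1. Which data are lost, by timing (Sections 6 and 9, schedule).**
- Before the post-treatment visit: the post-treatment GRASSP, hence the participant's value in the main comparison, and all 4-week data.
- After the post-treatment visit: the 4-week data only. The main GRASSP change is already in hand, and the mixed model can still use the earlier observations.

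**2. Share of time after the last session.** The schedule does not state what its day numbers count from. Assume Day 0 is the last session, because Day 5 counted from baseline would fall inside the treatment weeks. Ten weekday sessions over two weeks span 12 calendar days. Take 1 to 7 days from baseline to the first session, and follow-up at day 30 to 40. Share = follow-up day / (gap + 12 + follow-up day).
- Lowest: 30 / (7 + 12 + 30) = 30/49 = 61.2%.
- Highest: 40 / (1 + 12 + 40) = 40/53 = 75.5%.

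This is a share of calendar time, not a probability of losing data.

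**3. Attrition limit of 10% per arm (Section 4).**
- Sham: 1/12 = 8.3% passes; 2/12 = 16.7% fails.
- Active: 1/24 = 4.2% and 2/24 = 8.3% pass; 3/24 = 12.5% fails.

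One such withdrawal uses the whole sham allowance or half of the active one.

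**4. Chance of breaching the limit, if one such withdrawal occurs.** Other drop-out is assumed independent with probability d. Without the withdrawal, the chance is P(X ≥ 2) with X ~ Bin(12, d) for sham and P(X ≥ 3) with X ~ Bin(24, d) for active. With it, the chance is P(X ≥ 1) with X ~ Bin(11, d) and P(X ≥ 2) with X ~ Bin(23, d).

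| Assumed d | Sham, without | Sham, with one | Active, without | Active, with one |
|---|---|---|---|---|
| 3% | 4.9% | 28.5% | 3.4% | 15.1% |
| 5% | 11.8% | 43.1% | 11.6% | 32.1% |
| 10% | 34.1% | 68.6% | 43.6% | 68.5% |

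Example, sham at 5%: 1 − 0.95^11 = 43.1%.

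**5. Power for the main comparison, if one post-treatment GRASSP is lost.** Normal approximation, two-sided 5% (assumed), standardised effect δ (assumed): power = Φ(δ/√(1/n_active + 1/n_sham) − 1.96).

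| δ | 24 and 12 | 24 and 11 | 23 and 12 |
|---|---|---|---|
| 0.8 | 61.9% | 59.4% | 61.3% |
| 1.0 | 80.7% | 78.4% | 80.2% |

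The largest fall is 61.9 − 59.4 = 2.5 points.

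**6. Sections 5 and 7 side by side.** Section 7 asks about pregnancy at screening and excludes pregnant women. The three exclusions in Section 5 do not name it, and the schedule has no row for it. The nearest Section 5 entry is the general inclusion item on contraindications to tDCS. The two sections are not worded to match.

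**The case against.** The strongest reply is that little turns on this. The rule is stated once, nothing contradicts it, and events will be few. One withdrawal breaches neither limit, and the effect on power is small. All of this stands, and it is why the point is minor. The consent pages are not in the text available here and may say something about follow-up after withdrawal; if so, the protocol should match them.

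A second reply concerns the remedy. Section 4 lists drop-outs as a measure of adherence with therapy and does not define the term. Simply not counting a participant who stopped the intervention would alter a feasibility endpoint and could flatter the programme. This also stands, and the fix is framed accordingly.

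A reader might infer more than the documents support:
- *That scheduled tDCS safety follow-up is lost after session 10.* No side-effects form is scheduled then. Someone who conceives after the last session was not stimulated while pregnant, and 12 of the 36 participants receive sham. What could be lost is mainly serious adverse event information, with the medication checklist and the ASIA scale.
- *That the main GRASSP comparison is always lost.* It is lost only if the withdrawal precedes the post-treatment visit.
- *That pregnant women may be enrolled because Section 5 does not list pregnancy.* Section 7 asks and excludes at screening, and this is a single-site study. The gap is one of cross-referencing.
- *That Section 7 makes anyone who dislikes a question leave.* The sentence "If subjects feel uncomfortable in answering any of the questions they may stop the study at any time" gives a permission; it does not forbid skipping a question.

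**Conclusion.** The point holds as a minor one. Read plainly, Section 7 ends data collection for a reason that bears on stimulation alone, and it does so even at visits when no stimulation remains. The cost per case is the 4-week data, plus the post-treatment GRASSP if the timing is early, and one loss against an allowance of one (sham) or two (active).

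The breach probabilities are conditional on such a withdrawal having occurred and rest on assumed rates of other drop-out. The power figures rest on assumed effects and a two-sided 5% level. Neither is a forecast, because the documents give no pregnancy rate. The conclusion also assumes that withdrawal from the study ends assessments: no passage says otherwise, though none expressly halts data collection. Whether stimulation or training should stop is a clinical matter and is not judged here.

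**What to change.** In Section 7, leave the decision on stopping stimulation or training with the sponsor, and add that ending treatment under this rule does not end data collection. A participant who agrees completes the remaining scheduled assessments (GRASSP, grip strength, SCIM, fNIRS and the other items due at those visits), and any serious adverse events continue to be recorded.

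In Sections 4 and 9, report these cases separately by arm, and give the attrition result both with and without them. The feasibility criterion then stays intact and the reader can see what a protocol-imposed withdrawal contributed.

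Editorially, reconcile the Section 5 exclusion list with the Section 7 statement on pregnancy, so that eligibility can be checked from one place.

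The cost is protocol and consent wording and one extra line of reporting. No visit or procedure is added to the schedule.
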